### 2.1. Modifications to the Analysis Plan Described in the Protocol

PK concentration and parameters pertaining to Tasso OnePlus micro sampling will be regarded as results from serum etrasimod in summary tables and listings, while PK concentration and parameters derived from venous sampling will be regarded as results from plasma etrasimod.

### 2.2. Study Objectives, Endpoints, and Estimands

The following are the objectives and endpoints in this study. Estimand framework will not be applied to this Phase 1 study in healthy participants.

Objectives	Endpoints	
Primary:	Primary:	
• To compare the PK of etrasimod 2 mg clinical IR tablets under fasted conditions in healthy participants using Tasso OnePlus PK micro samples taken by participants only (Treatment G) vs. CRU staff and participants (Treatment F) in a hybrid DCT design	
 
Plasma AUC24hr, AUC24hr-last, AUCinf (if data permit, otherwise AUClast) and Cmax of etrasimod
 
	
Secondary:	Secondary:	

 
To compare the PK of etrasimod 2 mg clinical IR tablets under fasted conditions in healthy participants using Tasso OnePlus PK micro samples taken by participants only (Treatment G) vs. CRU staff and participants (Treatment F) in a hybrid DCT design vs. venous PK samples taken by CRU staff in conventional design of main study (Treatment A)
 
	
 
Plasma AUC24 hr, AUC24hr-last, AUCinf (if data permit, otherwise AUClast) and Cmax of etrasimod
 
	

 
To evaluate the safety and tolerability of etrasimod 2 mg clinical IR tablets in healthy participants using mobile wearable devices in a hybrid DCT design
 
	
 
Assessment of first dose HR reduction, TEAEs, clinical laboratory abnormalities, vital signs, PEs, and ECGs
 
	
Tertiary/Exploratory:	Tertiary/Exploratory:	

 
To compare the concentrations of etrasimod in PK samples collected using Tasso OnePlus micro sampling device against those using venous blood sampling.
 
	• Plasma concentrations of etrasimod obtained via micro sampling compared to venous sampling at pre-dose and at 2 and 4 hrs post-dose.	

# 2.3. Study Design

This is a Phase 1, open-label, single-dose, fixed-sequence, crossover study in a single cohort of approximately 8 healthy male or female participants conducted using a hybrid DCT design.

The study will consist of 2 treatments. Participants will receive the two Treatments F and G in a fixed sequence as shown below. There will be an 8-day washout between each dose.

Fixed Treatment Sequence (n=8)	Period 1	Period 2
1	F	G

Treatment F: Single oral dose of etrasimod 2 mg, DCT with practice sessions\* (Reference)

Treatment G: Single oral dose of etrasimod 2 mg, DCT without practice sessions\*\* (Test)

\* Practice of Tasso and Wearable Monitoring Devices on Day 2 at CRU; participant self-assessment remotely for vitals and ECG (Days 3-5) and PK samples (Days 3-8)

\*\* Participant self-assessment using Tasso and Wearable Monitoring Devices on Days 1-2 at CRU; and remotely on Days 3-8

## 3. ENDPOINTS AND BASELINE VARIABLES: DEFINITIONS AND CONVENTIONS

## 3.1. Primary Endpoints

The primary endpoints are the plasma AUC24hr, AUC24hr-last, AUCinf (if data permit, otherwise AUClast) and Cmax of etrasimod. The test/reference ratios for AUC24 hr, AUC24hr-last, AUCinf, AUClast and Cmax will be derived with Treatment G (etrasimod 2 mg, DCT Tasso PK micro samples taken by participants only) as the test treatment and Treatment F (etrasimod 2 mg, DCT Tasso PK micro samples taken by CRU staff and participants) as the reference treatment.

Plasma PK parameters of etrasimod will be derived (as data permit) from the concentration-time data using standard noncompartmental methods as outlined in the Table 2 below. Actual PK sampling times will be used in the derivation of PK parameters. In the case that actual PK sampling times are not available, nominal PK sampling time will be used in the derivation of PK parameters.

Parameter	Definition	Method of Determination
AUC inf	Area under the concentration-time curve from time zero extrapolated to infinity	AUC last + (C last */k el ), where C last * is the predicted plasma concentration at the last quantifiable time point from the log-linear regression analysis
AUC last	Area under the plasma concentration-time profile from time zero to the time of the last quantifiable concentration (C last )	Linear/Log trapezoidal method.
AUC 24hr	Area under the plasma concentration-time profile from time zero to 24 hr	Linear/Log trapezoidal method.
AUC 24hr-last	Area under the plasma concentration-time profile from time 24 hr to the time of the last quantifiable concentration (C last )	Linear/Log trapezoidal method.
C max	Maximum observed concentration	Observed directly from data

#### Table 2. Definitions of PK Parameters

### 3.2. Secondary Endpoints

### 3.2.1. PK Parameters from Tasso and Venous Blood Sampling

The test/reference ratios for AUC24hr, AUC24hr-last, AUCinf, AUClast and Cmax will be derived with Treatment A (etrasimod 2 mg, Main study, venous PK samples) as the Reference treatment while Treatment F (etrasimod 2 mg, DCT Tasso PK micro samples taken by CRU staff and participants) and Treatment G (etrasimod 2 mg, DCT Tasso PK micro samples taken by participants only) as the Test treatments.

### 3.2.2. Safety Endpoints

The following data are considered in standard safety summaries (see protocol for collection days, baseline assessment, and list of parameters):

- first dose HR reduction
- adverse events (AE)

- laboratory data
- vital signs data
- electrocardiogram (ECG) results

## 3.2.2.1. First Dose HR reduction

For all periods, HR will be measured every hour up to 6 hours, at 8 and 24 hours postetrasimod dose at Day 1. The baseline HR value is the average of the HR values from the triplicate ECG measurements collected predose on Day 1 of each period. Changes from baseline will be defined as the change between the postdose measurements and baseline value. In addition, the nadir HR value on Day 1 will be derived.

## 3.2.2.2. Adverse Events

Any adverse events occurring following start of treatment will be considered as treatment emergent adverse event (TEAE). Events that occur during follow-up within the lag time of up to 35 days after the last dose of study intervention will be counted as treatment emergent and attributed to the last treatment taken. The time period for collecting AEs ("active collection period") for each participant begins from the time the participant provides informed consent.

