1.2. Schema

1.3. Schedule of Activities

The SoA table provides an overview of the protocol visits and procedures. Refer to the STUDY ASSESSMENTS AND PROCEDURES section of the protocol for detailed information on each procedure and assessment required for compliance with the protocol.

The investigator may schedule visits (unplanned visits) in addition to those listed in the SoA table, in order to conduct evaluations or assessments required to protect the well-being of the participant.

Table 1. Study Schedule of Assessment

Visit Identifier Abbreviations used in this table may be found in Appendix 10	Screen		Per	iods 1-2		F/U Telephone Contact	ET	Notes
Days Relative to Day 1 in Each Period	Day -28 to Day -2	Day -1	Day 1	Day 2	Days 3-8	Days 28-35*		 Participants will be screened within 28 days of the first dose of study intervention. * Follow-up contact will occur by telephone and must occur at least 28 to 35 days after the last administration of etrasimod (Day 1 of Period 2 if dosing completed).
Period 1 Study Days	-28 to -2	-1	1	2	3-8			Participants will be discharged from CRU on Day 2 of Period 1
Period 2 Study Days		9	10	11	12-17			 Minimum 8-day washout period between dosing in Periods 1 and 2 Participants will be discharged from CRU on Day 2 of Period 2.
Check In		X						
Informed consent	X							
Inclusion/exclusion criteria	X	X						Inclusion/exclusion criteria should be reviewed and updated on Day -1 of Period 1 only.
CRU confinement		X	\rightarrow					Participants will be discharged from CRU on Day 2 of Periods 1 and 2
Demography	X							Including measurement of height and weight
Medical/medication history, drug, tobacco, and alcohol history	X	X						 Include history of alcohol abuse, tobacco/nicotine containing products, licit and illicit drug use or dependence within 6 months of screening. For Day -1, records should be reviewed or updated only.

Table 1. **Study Schedule of Assessment**

Visit Identifier Abbreviations used in this table may be found in Appendix 10	Screen		Pe	riods 1-2		F/U Telephone Contact	ET	Notes
Days Relative to Day 1 in Each Period	Day -28 to Day -2	Day -1	Day 1	Day 2	Days 3-8	Days 28-35*		 Participants will be screened within 28 days of the first dose of study intervention. * Follow-up contact will occur by telephone and must occur at least 28 to 35 days after the last administration of etrasimod (Day 1 of Period 2 if dosing completed).

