In both Periods 1 and 2, capillary blood samples (using micro sampling Tasso device) for PK analysis will be collected at predose and at 1, 2, 4, 6, 8, 12, 24, 48, 72, 96, 120, 144 and 168 hours postdose (SoA). Venous blood samples for PK analysis will be collected predose and at 2 and 4 hours postdose (SoA). Micro PK sampling occurs after venous PK blood sampling; samples will be taken from the alternate arms from one sampling time to the next.

Participants will be screened within 28 days of the first dose of study intervention and if all entry criteria are fulfilled, the participants will report to the CRU on the day prior to Day 1 dosing (Day -1). On Day 1 of each period, participants will receive a single dose of study intervention at the CRU. Administration of etrasimod will be oral via dosing of clinical IR

Treatment G: Single oral dose of etrasimod 2 mg, DCT without practice sessions** (Test)

^{*} Practice of Tasso and Wearable Monitoring Devices on Day 2 at CRU; participant self-assessment remotely for vitals and ECG (Days 3-5) and PK samples (Days 3-8)

^{**} Participant self-assessment using Tasso and Wearable Monitoring Devices on Days 1-2 at CRU; and remotely on Days 3-8

tablet 2 mg with water as per dosing instructions. Participants will be fasted for at least 10 hours predosing and 4 hours postdosing.

Participants will be confined in the CRU for a total of at least 2 days and discharged on Day 2 of each Period. A follow-up phone call will be made at least 28 calendar days and up to 35 calendar days after the last administration of the study intervention to capture any potential AEs and confirm appropriate contraceptive usage.

Tolerability and safety will be assessed for all treatments by monitoring AEs. Participants who withdraw from the study or whose PK samples are determined to be non-analyzable may be replaced at the discretion of the of the investigator upon consultation with the sponsor.

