8.4.1. Time Period and Frequency for Collecting AE and SAE Information

The time period for actively eliciting and collecting AEs and SAEs ("active collection period") for each participant begins from the time the participant provides informed consent, which is obtained before undergoing any study-related procedure and/or receiving study intervention), through and including a minimum of 28 calendar days after the last administration of the study intervention.

Follow-up by the investigator continues throughout the active collection period and until the AE or SAE or its sequelae resolve or stabilize at a level acceptable to the investigator.

When a clinically important AE remains ongoing at the end of the active collection period, follow-up by the investigator continues until the AE or SAE or its sequelae resolve or stabilize at a level acceptable to the investigator and Pfizer concurs with that assessment.

For participants who are screen failures, the active collection period ends when screen failure status is determined.

If the participant withdraws from the study and also withdraws consent for the collection of future information, the active collection period ends when consent is withdrawn.

If a participant permanently discontinues or temporarily discontinues study intervention because of an AE or SAE, the AE or SAE must be recorded on the CRF and the SAE reported using the CT SAE Report Form.

Investigators are not obligated to actively seek information on AEs or SAEs after the participant has concluded study participation. However, if the investigator learns of any SAE, including a death, at any time after a participant has completed the study, and they consider the event to be reasonably related to the study intervention, the investigator must promptly report the SAE to Pfizer using the CT SAE Report Form.

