#### 6.2.2.2. Adverse Events

TEAEs will be reported in accordance with the CaPS.

Participant discontinuations due to adverse events will be detailed by treatment. Data will be reported in accordance with the CaPS.

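### With a fixed F-then-G order, the rule for follow-up adverse events gives Treatment G 28 to 35 days at risk against about 9 for Treatment F, so TEAE counts by treatment are not on an equal footing

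*SAP*

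**What the plan says.** SAP 2.3 fixes the order: "Participants will receive the two Treatments F and G in a fixed sequence as shown below", with F in Period 1 and G in Period 2.

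SAP 3.2.2.2 treats any event after the start of treatment as treatment emergent. It extends this to follow-up events "within the lag time of up to 35 days after the last dose of study intervention", which "will be counted as treatment emergent and attributed to the last treatment taken".

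Three places in the protocol set the window lengths:
- Section 1.3, row "Period 2 Study Days", puts the Period 2 dose on study Day 10. The accompanying note reads "Minimum 8-day washout period between dosing in Periods 1 and 2".
- Section 4.1 places the closing telephone call "at least 28 calendar days and up to 35 calendar days after the last administration of the study intervention".
- Section 8.4.1 keeps active collection open "through and including a minimum of 28 calendar days after the last administration of the study intervention".

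SAP 6.2.2.2 leaves TEAE reporting to the sponsor's reporting standards (CaPS). The only adverse-event output that it explicitly splits is this one: "Participant discontinuations due to adverse events will be detailed by treatment". Neither document gives an equal window, a rate per person-day or a separate follow-up category.

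**The concern.** Attributing follow-up events to the last treatment is an ordinary crossover convention. It is tolerable when the last treatment differs between sequences, because the long tail is then shared among treatments. Here there is one sequence. For completers the tail always lands on G, and the imbalance cannot average out.

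Safety and tolerability in the hybrid design is a secondary objective. F and G are the same 2 mg dose and differ in order and in who performs the assessments on Days 1 and 2. If event counts for the two are set next to each other, a reader will look for an explanation in those differences, when unequal time at risk alone could produce the gap.

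**Working it through.** **Check of the schedule.** Screening of 28 days, plus 9 days from study Day 1 to Day 10, plus 28 days to the earliest call, is 65 days or 9.3 weeks. This agrees with the stated total of about 9 weeks. A call at day 35 gives 72 days, or 10.3 weeks.

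**Time at risk, 8 completers.**
- F: study Day 1 to the Period 2 dose on Day 10 = 9 days; 8 × 9 = 72 person-days.
- G: 28 to 35 days; 8 × 28 = 224 to 8 × 35 = 280 person-days.

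**Expected ratio at one constant daily rate.** The rate cancels: 28/9 = 3.1 and 35/9 = 3.9. The share of all TEAEs placed under G is 28/37 = 76% to 35/44 = 80%, against 50% with equal windows. If the doses were only the minimum 8 days apart, the ratio would be 3.5 to 4.4; a longer gap would lower it.

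**How often G would exceed F.** The documents give no event rate, so the rates below are assumptions. Counts are taken as independent Poisson with mean 8 × days × rate, and G runs for 35 days.

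| Assumed events per person-day | Expected F | Expected G | P(G > F) | Tie | P(F > G) |
|---|---|---|---|---|---|
| 0.0025 | 0.18 | 0.70 | 44.4% | 46.9% | 8.7% |
| 0.005 | 0.36 | 1.40 | 63.6% | 27.0% | 9.4% |
| 0.01 | 0.72 | 2.80 | 80.4% | 12.7% | 6.9% |
| 0.02 | 1.44 | 5.60 | 92.5% | 4.4% | 3.1% |
| 0.05 | 3.60 | 14.0 | 99.3% | 0.4% | 0.3% |

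The chance that a participant has at least one TEAE is 1 − exp(−rate × days). At 0.01 per day it is 8.6% under F and 29.5% under G; at 0.02 it is 16.5% and 50.3%.

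**Dilution by acute events.** Events soon after dosing fall inside both windows. With *a* acute events per dose (assumed) and background rate *r*, the ratio is (a + 35r)/(a + 9r). At r = 0.01:
- a = 0.1: 0.45/0.19 = 2.4
- a = 0.3: 0.65/0.39 = 1.7
- a = 1: 1.35/1.09 = 1.2

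**What would cancel it.** The excess of background events under G is (35 − 9) × r per participant, which is 0.26 at r = 0.01. That many additional first-dose events per participant in F would offset it.

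**What the extra days contain.** With the stated half-life of about 30 hours, 9 days is 216/30 = 7.2 half-lives, leaving 0.5^7.2 = 0.7% of drug. About 26 of the 35 days under G are therefore almost drug-free.

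**The case against.** The strongest reply is that a constant daily rate does not suit a single dose of this drug. Protocol 2.2.4.2 and 2.3.1 describe the heart-rate effect as largest at the first dose, and the first dose is always F. That pushes counts towards F. This stands: 3.9 is not a forecast, and the acute-event calculation belongs beside it.

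Event capture is also uneven. Diaries and participant recording cover the remote days through Day 8 of each period. After Day 8 of Period 2 the only scheduled contact is the closing call. Fewer events may be picked up then, which would shrink the excess. This stands too, though the documents do not let one quantify it.

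Some of the premise is inferred. CaPS is not in the documents, so its table layout is unknown. A TEAE table by treatment is implied because an attribution rule has little other use. The end of the F window at the Period 2 dose is the natural reading, but the SAP states attribution explicitly only for follow-up after the last dose. A participant who stops after F carries the follow-up under F.

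Finally, the safety objective is to evaluate, not to compare F with G. No hypothesis is tested, and safety is descriptive. That limits the consequence but does not equalise the windows.

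A reader might go further and infer that the tables would suggest self-assessment carries or detects more events. The documents do not support that. F is also self-assessed remotely on Days 3 to 8, events are collected in the same way in both periods, and the late follow-up days are not self-assessment days. The plan draws no such conclusion from event counts.

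**Conclusion.** The point holds as a systematic imbalance in time at risk: about 9 days for F and 28 to 35 for G among completers. At an identical constant background rate the expected G:F ratio is 3.1 to 3.9, falling to about 1.7 under the assumed mix of 0.3 acute events per dose and 0.01 per day.

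It would be too strong to say that the counts will favour G. With 8 participants the chance that G exceeds F is 64% at an assumed 0.005 events per day and 80% at 0.01, before allowing for first-dose effects or weaker late capture. A tie or reversal is possible.

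The size rests on an assumed rate, equal capture throughout, everyone completing both periods, and a by-treatment table that is implied but not shown. No test or sample size is affected. This is a cheap improvement to the summary of a secondary objective.

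**What to change.** In SAP 6.2.2.2, add a summary of TEAEs by treatment restricted to onset from the dose to the end of Day 8 in each period. Show later-onset events in a separate column according to the period in which they start:
- after Day 8 of Period 1 and before the Period 2 dose (study Day 9 as scheduled): Period 1;
- after Day 8 of Period 2: follow-up.

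Leave the TEAE definition, the overall TEAE summary and the listing as they are, so that no event is lost.

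The cost is one extra table and a short addition to the SAP, using data already collected. The common window ends where participant recording ends in both periods, so capture is more alike as well. It does not remove the period effect: F is still always the first dose and G the second, and any remaining difference must be read with that in mind.

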## 3.2.2.3. Laboratory Data

Safety laboratory tests will be performed as described in the protocol.

For all periods, the baseline measurement is the predose measurement on Day -1 in each period. Changes from baseline will be defined as the change between the postdose and baseline measurements.

### 3.2.2.4. Vital Signs

Supine blood pressure (BP), pulse rate (PR) and temperature will be measured at times specified in the SoA given in the protocol.

For all periods, the baseline measurement is the predose measurement on Day 1 in each period. Changes from baseline will be defined as the change between the postdose and baseline measurements.

### 3.2.2.5. Electrocardiograms

QT interval, QTcF, PR interval, QRS and heart rate (HR) will be recorded at each 12-lead ECG assessment time indicated in the SoA given in the protocol. QTcF will be derived using Fridericia's heart rate correction formula:

 $QTcF = QT / (RR)^{(1/3)}$  where RR = 60/HR (if not provided)

For all periods, the baseline value is the average of triplicate ECG measurements collected predose on Day 1 of each period. Changes from baseline will be defined as the change between the postdose measurements and baseline value.

# 3.3. Other Safety Endpoint(s)

None.

PFIZER CONFIDENTIAL DMB02-GSOP-RF02 8.0 Statistical Analysis Plan Template TMF Doc ID: 98.03 Page 7 of 16

### 3.4. Exploratory Endpoint

Plasma concentrations of etrasimod obtained via micro sampling (taken by participants only and taken by CRU staff and participants) compared to venous sampling at predose and at 2 and 4 hours postdose.

### 3.5. Baseline Variables

Baseline characteristics will be collected according to the schedule of activities (SoA) as specified in the protocol.

## 4. ANALYSIS SETS (POPULATIONS FOR ANALYSIS)

Data for all participants will be assessed to determine if participants meet the criteria for inclusion in each analysis population prior to releasing the database and classifications will be documented per standard operating procedures.

Participant Analysis Set	Description
Safety Analysis Set	All participants who take at least 1 dose of study intervention. Participants will be analyzed according to the product they actually received.
PK Concentration Set	All participants who take at least 1 dose of study intervention and in whom at least 1 concentration value is reported.
PK Parameter Set	All participants who take at least 1 dose of study intervention and in whom at least 1 of the PK parameters of interest are reported.

### 5. GENERAL METHODOLOGY AND CONVENTIONS

Final analysis will be performed after study participant data set release following last participant last visit.

#### 5.1. Hypotheses and Decision Rules

No statistical hypothesis will be tested in this study.

#### 5.2. General Methods

#### 5.2.1. Analyses for Binary/Categorical Endpoints

For binary or categorical variables, number of participants, numbers and percentages of participants meeting the categorical criteria will be presented in accordance with the Clinical Data Interchange Standards Consortium and Pfizer Standards (CaPS).

### 5.2.2. Analyses for Continuous Endpoints

For continuous variables, the data will be summarized using the number of participants, mean, median, standard deviation (SD), minimum, and maximum in accordance with the CaPS. For appropriate PK parameters, geometric mean and geometric coefficient of variation (%CV) will also be summarized.

